3 STUDY DESIGN

3.1 Study Design

The study will be a Phase 1, open-label, multiple-dose, PK, safety, and tolerability study in children aged 4 to 5 years diagnosed with ADHD. Enrollment will be stratified by gender to ensure that at least 2 of the 10 subjects expected to complete the rich PK sampling portion of the study and at least 3 of the 10 subjects expected to complete the sparse PK sampling portion of the study are females. Subjects for the rich PK sampling portion of the study will be enrolled first. Once the required number of subject is achieved, enrollment in the sparse PK sampling group will begin.

Subjects will be assessed for eligibility during the screening period. The duration of the screening period will be a maximum of 32 days. If subjects are currently taking ADHD medication, they are required to discontinue their current ADHD medication at least 7 days prior to the first dose of investigational product on Day 1 of Week 1 (washout period).

Following the screening visit, eligible subjects will return to the clinical research center (CRC) on Day 1 of Week 1 to reconfirm eligibility criteria and enter into the treatment phase.

If more than 32 days have elapsed since the screening evaluations were completed, then the following evaluations must be repeated at baseline (prior to the first dose of investigational product on Day 1 of Week 1): vital signs, clinical laboratory evaluations, blood pressure, electrocardiograms (ECGs), weight, and height. The physical examination will be abbreviated with a review of the following body systems: general appearance, respiratory, and cardiovascular.

The PK of *d*-amphetamine and *l*-amphetamine will be evaluated in this study, according to the schedule in [Table 1](#) (rich PK sample subset) and [Table 2](#) (sparse PK sample subset).

Rich PK Sample Scheme (9 Samples/Subject) Collection

Predose PK samples will be collected on Day 1 of Week 1, and serial blood samples for PK analysis will be drawn prior to dosing on Day 7 of Week 4 (within 60 minutes prior to dosing) and up to 48 hours after administration of the investigational product.

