11. Subject has any clinically significant ECG or clinically significant laboratory abnormalities at the first screening visit based on the investigator's judgment. A single retest of laboratory parameters is allowed based on the investigator's judgment.
12. Subject has Marfan's syndrome.
13. Subject has a blood pressure \geq 95th percentile for age, sex, and height at the screening visit ([Appendix 2.3](#) and [Appendix 2.5](#)).
14. Subject has a height \leq 5th percentile for age and sex at the first screening visit ([Appendix 2.2](#) and [Appendix 2.4](#)).
15. Subject has a weight \leq 5th percentile for age and sex at the first screening visit.
16. Subject has current abnormal thyroid function test results, defined as abnormal thyroid-stimulating hormone, thyroxine (T4), and tri-iodothyronine (T3) at the first screening visit. Treatment with a stable dose of thyroid medication for at least 3 months is permitted.
17. Subject has a history of seizures (other than infantile febrile seizures).
18. Subject has a current, controlled (requiring medication or therapy) or uncontrolled, comorbid psychiatric disorder including but not limited to any of the following comorbid Axis I disorders and Axis II disorders:
 - Post-traumatic stress disorder or adjustment disorder
 - Bipolar illness, psychosis/schizophrenia, or positive family history of these disorders in first- or second-degree relatives
 - Pervasive developmental disorder
 - Obsessive-compulsive disorder
 - A serious tic disorder, or a family history of Tourette disorder
 - Substance abuse or dependence disorder
 - Any other disorder that, in the opinion of the investigator, contraindicates SHP465 or amphetamine treatment or confounds efficacy or safety assessments.
19. Subject is currently considered a suicide risk in the opinion of the investigator, has previously made a suicide attempt, or has a prior history of or is currently demonstrating active suicidal ideation.
20. Subject has a history of physical, sexual, or emotional abuse.
21. Subject has a primary sleep disorder (eg, sleep apnea, narcolepsy).
22. Subject has a history or is currently diagnosed with an eating disorder.

23. Subject has a clinically important abnormality on the urine drug and alcohol screen (excluding the subject's current ADHD stimulant, if applicable) at the first screening visit.
24. Subject lives with anyone who currently abuses stimulants or cocaine, based on the investigator's judgment.

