6.2.2 Dosing

There will be one SHP465 dose level of 6.25 mg used in this study.

On Day 1 of each week (Weeks 1-4), all subjects will report to the CRC approximately 2 hours prior to the time of dosing for predose evaluations. The dose will be administered daily as a single dose for 28 days (± 1 day) at 8:00 AM (± 1 hour). Doses on Day 1 of each week (Weeks 1-4) will be administered in the CRC. The parent/LAR will be dispensed a bottle containing the remaining doses for that week. The same parent/LAR should be available daily to dispense the dose of investigational product for the study duration.

For all subjects, investigational product will be taken by either swallowing the capsule whole or sprinkling the capsule contents onto 1 tablespoon of applesauce. The sprinkled applesauce should be consumed immediately; it should not be stored. Subjects should take the applesauce with sprinkled beads in its entirety without chewing. A single capsule cannot be split. The empty gelatinous capsule should be discarded.

On Day 7 of Week 4, subjects in the rich PK sampling subset will report to the CRC for dosing approximately 2 hours prior to dose administration. Subjects should fast for 2 hours prior to dose administration and for 2 hours postdose, and the site should record the timing and composition of the last meal consumed by the subject. Subjects in the rich PK sampling portion will be required to remain at the CRC through 8 hours postdose. At 2 hours postdose, subjects will be allowed to consume a light breakfast, eg, a single serving of cereal with up to 8 ounces of skim milk. Subjects should be well hydrated while at the CRC for PK draws. Water or other clear liquids should be given ad libitum. Caffeinated beverages should not be consumed for 2 hours prior to dosing and until 12 hours after the postdose PK sample is obtained.

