7.1.1 Screening and Washout Period

Subjects will be screened within 32 days prior to initiation of dosing of the investigational product. During the screening period, the eligibility of subjects will be assessed. All screening assessments and procedures are to be performed by the principal investigator or a qualified designee. A complete list of screening procedures to be performed is provided in [Table 1](#) for the rich PK sample subset and [Table 2](#) for the sparse PK sample subset.

The principal investigator or his/her designee must obtain written informed consent and assent from the subject's parent/LAR prior to any study-related procedures conducted during the screening period. There must also be documentation of assent (if required by the institutional review board [IRB]), indicating that the subject is aware of the investigational nature of the study and the required procedures and restrictions, prior to the performance of any study-related procedures.

If subjects are currently taking ADHD medication, they are to discontinue their current ADHD medication at least 7 days prior to the first dose of investigational product (please refer to Section [4.2](#) for additional information).

Screening procedures may take place across multiple days to allow enough time to complete all procedures and confirm initial subject eligibility. Screening procedures and dates should be well documented in the source documents. The date of the screening visit is the date the parent/LAR has signed informed consent for this study.

A screen failure is a subject who has given informed consent and failed to meet any of the inclusion and/or met at least 1 of the exclusion criteria and has not been enrolled or administered investigational product(s).

Subjects cannot be rescreened once they have been designated as a definite screen failure. Reassessment of subjects who failed specific inclusion/exclusion criteria is not allowed.

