APPENDIX 2.3 BLOOD PRESSURE LEVELS FOR BOYS BY AGE AND HEIGHT PERCENTILE

To determine the eligibility of a male subject for entry in the study (based on the study inclusion criteria), first determine the percentile of height for the subject based on their age (as a whole number based on the subject's last birthday; [Appendix 2.2](#)). For subjects who fall between the 2 height percentiles, use the lower of the 2 percentiles. Once the subject's age and height percentile for age are determined, use the following table to determine eligibility.

All blood pressure values listed as follows are 95th percentile for age and height percentile. The subject's systolic and diastolic blood pressure readings at the screening visit and the baseline visit (predose on Day 1) must not exceed the following corresponding table value for their age and height percentile.

Age (Year)	Systolic Blood Pressure (mmHg)							Diastolic Blood Pressure (mmHg)						
	← Percentile of Height →							← Percentile of Height →						
	5%	10%	25%	50%	75%	90%	95%	5%	10%	25%	50%	75%	90%	95%
4	106	107	109	111	112	114	115	66	67	68	69	70	71	71
5	108	109	110	112	114	115	116	60	70	71	72	73	74	74
6	109	110	112	114	115	117	117	72	72	73	74	75	76	76

Source: National Heart Lung and Blood Institute; May 2004

http://www.nhlbi.nih.gov/guidelines/hypertension/child_tbl.htm

[figure not shown]

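### Exclusion 13 and Appendices 2.3/2.5 disagree on the visit and the boundary for the blood-pressure limit, and the repeat tests required after 32 days are tied to no numbered criterion

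*Protocol*

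**What the plan says.** **Blood pressure.** Exclusion 13 (Protocol 4.2 and synopsis) excludes a child whose blood pressure is at or above the 95th percentile for age, sex and height, and names the screening visit only. In 4.2 it points to Appendices 2.3 (boys) and 2.5 (girls). Both appendices state that the child's "blood pressure readings at the screening visit and the baseline visit (predose on Day 1) must not exceed" the tabulated 95th-percentile value. Tables 1 and 2 schedule vital signs on Day 1 in both sampling portions.

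**Screening window.** Protocol 7.1.1 says: "Subjects will be screened within 32 days prior to initiation of dosing of the investigational product". Sections 3.1 and 3.2 give the same 32-day maximum. Section 3.1 then adds: "If more than 32 days have elapsed since the screening evaluations were completed, then the following evaluations must be repeated at baseline". The list covers vital signs, laboratory tests, blood pressure, ECG, weight and height, before the first dose. The laboratory panel in 7.2.2.5 includes the thyroid tests.

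**Criteria that would use those results.** Exclusion 11 (ECG and laboratory) refers to "clinically significant laboratory abnormalities at the first screening visit". Exclusions 14 (height), 15 (weight) and 16 (thyroid) are tied to the first screening visit in the same way.

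**After dosing.** Section 4.4.1.1 requires further evaluation if average systolic or diastolic pressure rises more than 15 mmHg from the Day 1 predose value, or if it is at or above the 95th percentile. If the child stays in the study and the criterion is still met at the unscheduled visit, the child is discontinued. Section 4.4.2 lists blood pressure as a reason for discontinuation. SAP 11.3 tabulates, by sex, children with any post-baseline value strictly above the 95th percentile. Its denominator is every child of that sex in the safety set with a post-baseline measurement.

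**The concern.** A numerical safety threshold for entry should give the same answer wherever a site looks it up. Here about 10 sites can apply two different rules to the same Day 1 reading, and two different boundaries to the same screening reading.

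The difference also reaches the safety results. The 4.4.1.1 trigger can be met on level alone, and the SAP table counts level alone. A child admitted above the limit can appear in both with an unchanged blood pressure. In an uncontrolled study with so few children, such a case can be read as a drug effect.

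The repeat-test provision raises a related question. It requires measurements before dosing but does not connect them to the exclusions they would inform, and it applies only after a point that the protocol elsewhere says screening will not pass.

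**Working it through.** No statistical figure in the plan depends on this, so the check sets the passages side by side and adds two short counts.

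**1. Which readings decide eligibility?** Take a boy aged 4 at the 50th height percentile. Appendix 2.3 and SAP Table 8 both give a systolic limit of 111 mmHg. The readings are illustrative.

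| Case | Screening | Day 1 predose | Exclusion 13 as worded | Appendix 2.3 |
|---|---|---|---|---|
| A | below 111 | 112 | not excluded | not eligible |
| B | 111 | below 111 | excluded | eligible |
| C | below 111 | 111 | not excluded | eligible |

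Case A is the visit conflict. Case B is the boundary conflict (at or above, against above).

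**2. What happens on treatment if the reading does not change?**

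- Case A: change = 112 − 112 = 0 mmHg, so the rise criterion is not met. But 112 ≥ 111, so 4.4.1.1 is triggered, and 112 > 111, so the child is counted in the SAP table.
- Case C: change = 111 − 111 = 0 mmHg. Since 111 ≥ 111, 4.4.1.1 is triggered, but 111 is not above 111, so the SAP table does not count the child.

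The entry criterion and the 4.4.1.1 trigger use at or above; the appendices and the SAP count use strictly above.

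**3. Does the SAP remove children who were already high?** No. The blood-pressure denominator in 11.3 has no baseline condition. The ECG analysis in 11.4 does: its percentages are relative to children with a baseline that is not potentially clinically important.

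**4. How much can one child move the table?** The planned minimum of female completers is 2 (rich) + 3 (sparse) = 5. If those 5 girls form the denominator, one girl is 1/5 = 20% of the row. The actual denominator is girls in the safety set with a post-baseline reading, so the share falls if more are enrolled.

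**5. Does the more-than-32-day branch fit the protocol's own calendar?**

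- Screening at its maximum plus rich-portion treatment: 32 + 30 = 62 days; 62/7 = 8.9 weeks.
- Screening at its maximum, 28 dosing days and 7 days to follow-up: 32 + 28 + 7 = 67 days; 67/7 = 9.6 weeks.

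Section 3.2 states about 9 weeks as the maximum participation. That is used up with screening at 32 days, so the branch either is never reached or contradicts the cap.

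**6. If the branch is reached, what are the results judged against?** The repeated laboratory, thyroid, height and weight values correspond to exclusions 11 and 14 to 16, each of which names the first screening visit. No passage extends those criteria to a repeat. Weight is also measured on Day 1 in every child under Tables 1 and 2, so the question for exclusion 15 does not depend on the branch.

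**The case against.** The best case on the other side has several parts.

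- **Exclusion 13 cites the appendices.** A site that follows the reference will find the Day 1 requirement and may treat it as part of the criterion. This is a fair reading of the visit question, but it does not settle the boundary, and the criterion itself still names one visit.
- **Other routes act on Day 1.** A reader might infer that the Day 1 reconfirmation can exclude no one. The documents do not support that. Exclusions 5 to 7 are anchored to dosing, and 18, 19 and 24 to 26 can apply on Day 1. Section 7.2.2.7 rests ECG eligibility on the investigator's assessment without naming a visit, and 4.4 allows withdrawal at any time. Exclusions 25 and 26 and the withdrawal power are largely discretionary, so they soften the gap without supplying a numerical rule.
- **Day 1 as the only off-drug check.** This is also tempting, because screening precedes washout. It fails for never-medicated children, whom inclusion 6 admits and who are off drug at screening. For children on a stimulant, section 1.2 reports blood-pressure increases and weight decrease with SHP465, which suggests that an on-drug screening check is more likely to catch high pressure or low weight.
- **The laboratory retest.** "A single retest of laboratory parameters is allowed" under exclusion 11 might seem to collide with "Reassessment of subjects who failed specific inclusion/exclusion criteria is not allowed" in 7.1.1. The two can be read together, with the retest as a step before failure is declared. At most the wording could be clearer.
- **Laboratory turnaround.** Section 6.2.2 says "all subjects will report to the CRC approximately 2 hours prior to the time of dosing for predose evaluations", and nothing states when repeat results must be available. That is a silence, not a contradiction. Section 6.2.1 allocates the enrolled number just before dosing, once eligibility is determined.
- **Within 32 days the schedule is coherent.** Tables 1 and 2 plan no laboratory, thyroid or height measurement on Day 1, so for children inside the window exclusions 14 and 16 and the laboratory part of 11 match the schedule. This stands, and limits that part of the point to overruns.

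**Conclusion.** The point holds in two parts.

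First, exclusion 13 and Appendices 2.3/2.5 contradict each other on the visit and on the boundary. This concerns every child, because blood pressure is measured on Day 1 in all of the approximately 24 planned. A child above the limit on Day 1 can be eligible or not depending on the passage read and, if dosed, can meet 4.4.1.1 and the SAP count with no change on drug.

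Second, the 32-day cap and the more-than-32-day provision do not fit together, and the protocol does not say how laboratory, thyroid, height or weight results repeated under that provision bear on exclusions 11 and 14 to 16.

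The documents give no rate of Day 1 readings above the limit and no expected number of overruns, so the number of children affected cannot be estimated. The 20% figure assumes the minimum of 5 girls. The SAP introduction cites a protocol administrative change dated 31 October 2017 that is not among the documents; the conclusion assumes that it does not already resolve these passages.

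**What to change.** 1. Reconcile exclusion 13 (4.2 and synopsis) with Appendices 2.3 and 2.5 on the visit or visits at which the limit applies and on whether a value equal to the limit excludes, so that one rule applies at all sites.
2. Reconcile the 32-day cap in 3.1, 3.2 and 7.1.1 with the more-than-32-day provision in 3.1.
3. State whether results repeated under that provision are judged against exclusions 11 and 13 to 16 before the first dose.

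Which eligibility rule applies is for the sponsor to decide. The cost is amendment wording; no visit or measurement need be added, because Day 1 vital signs, weight and ECG are already scheduled. Depending on the rule chosen, there may be a few more screen failures on Day 1.

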4.3 Reproductive Potential

Contraception is not applicable as no female subjects in this study are of childbearing potential. All female subjects in this study are premenarchal, less than age 9 years, and Tanner Stage 1.

4.4 Discontinuation of Subjects

A subject may withdraw from the study, or the parent/LAR may withdraw the subject from the study, at any time for any reason without prejudice to their future medical care by the physician or at the institution. The investigator or sponsor may withdraw the subject at any time (eg, in the interest of subject safety). The investigator is encouraged to discuss withdrawal of a subject from investigational product with the medical monitor when possible.

If investigational product is discontinued, regardless of the reason, the early withdrawal evaluations listed in [Table 1](#) and [Table 2](#) are to be performed as completely as possible. Whenever possible, all discontinued subjects should also undergo the protocol-specified follow-up. Comments (spontaneous or elicited) or complaints made by the subject must be recorded in the source documents. The reason for termination, date of stopping investigational product, and the total amount of investigational product taken must also be recorded in the source document.

Subjects who discontinue may be replaced at the discretion of the investigator and sponsor to ensure at least 10 completers in each of the PK sampling portions of the study (of which at least 2 subjects in the rich PK sample subset and at least 3 subjects in the rich PK sample subset should be female).

4.4.1 Management of Blood Pressure and Pulse During the Study

To ensure that potential blood pressure and pulse increases associated with the use of SHP465 in this population are carefully monitored and appropriately managed, all subjects must be further evaluated if they meet any of the criteria defined in Sections [4.4.1.1](#) and [4.4.1.2](#).

4.4.1.2 Pulse

The resting pulse rate criterion for further evaluation has been defined based on the normative data presented in the National Health Statistics Report's "Resting Pulse Rate Reference Data for Children, Adolescents, and Adults: United States, 1999-2008" ([Ostchega et al., 2011](#)).

An elevation in the average (of 3 readings) sitting pulse, defined as >126 bpm, equivalent to the 99th percentile for this age range, requires further assessment.

The investigator will discuss each subject meeting this criterion with the medical monitor, and a joint decision between the investigator and the medical monitor will be made regarding continued participation in the study.

If the subject is allowed to remain in the study, an unscheduled visit will be conducted the next business day. If a visit cannot be scheduled the next business day, the subject may be discontinued from the study.

At the unscheduled visit, the investigator will notify the medical monitor of the results, and if the pulse is still >126 bpm, the subject will be discontinued from the study.

Any subject with a pulse rate \geq 126 bpm may be discontinued from the study based upon the clinical judgment of the investigator regarding the subject's safety.

4.4.2 Reasons for Discontinuation

The reason for withdrawal must be determined by the investigator and recorded in the subject's medical record and on the case report form (CRF). If a subject is withdrawn for more than 1 reason, each reason should be documented in the source document and the most clinically relevant reason should be entered on the CRF.

Reasons for discontinuation include but are not limited to:

- Adverse event (AE)
- Protocol violation
- Withdrawal by subject or parent/LAR
- Lost to follow-up
- Blood pressure and/or pulse criteria for discontinuation met
- Other (must be specified)

4.4.3 Subjects “Lost to Follow-up” Prior to Last Scheduled Visit

A minimum of 3 documented attempts must be made to contact any subject or parent/LAR in the event that any subject is lost to follow-up at any time point prior to the last scheduled contact (office visit or telephone contact). At least 1 of these documented attempts must include a written communication sent to the subject's last known address via courier or mail (with an acknowledgement of receipt request) asking that they return to the site for final safety evaluations and return any unused investigational product.

5 PRIOR AND CONCOMITANT TREATMENT

All nonstudy treatment (including but not limited to herbal treatments, vitamins, and nonpharmacological treatment such as behavioral treatment) received within 30 days prior to the screening visit (Day -1) (or PK equivalent of 5 half-lives, whichever is longer) and through the final study contact (including the protocol-defined follow-up period) must be recorded in the source document.

